#### 5.7.3.8 *Extra Bone Growth*

The percentage of participants with any extra bone growth (associated or not with a flare-up) since the previous visit will be presented for each visit with descriptive statistics. The number of extra bone growths since the previous visit will be calculated by totalling the number of distinct records (based upon the start date) within each of the visit windows as defined in section 6.1.

The location (and associated restricted movement if collected), the cause/proceed by, the number preceded by symptoms and the duration of bone growth will be presented in a listings. The duration of the bone growth will be defined as  $(\text{date of end of bone growth} - \text{date of start of bone growth} + 1)$ .

#### 5.7.4 *Analysis of Exploratory Endpoints*

No exploratory endpoints are defined for this study.

### 5.8 Safety

#### 5.8.1 *General Consideration*

All safety summaries and analyses will be based upon the FAS/SAS.

All analyses will be performed overall and by treatment regimen (chronic treatment only, flare-up treatment only, chronic and flare-up treatment).

All safety data will be included in participant data listings (see listing detail conventions in Appendix A5).

#### 5.8.2 *Extent of exposure*

Duration of total treatment, duration of flare-up treatment, mean duration of flare-up treatment and duration of chronic treatment will be summarised for the FAS/SAS with descriptive statistics. In the eCRF Dosing Form, for each treatment period, only the start date if completed (no end date). So, for each period, the end date will be considered as the start date of the following period (periods have to be sorted by start date) – 1. For the last record, it will be the date of last dose if collected, or if not the date of last contact. The date of last contact will be the latest date available across all assessments.

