Unit Dose Strength(s)	Each capsule contains 1 mg, 1.5 mg, 2.5 mg, 5 mg or 10 mg of palovarotene as active ingredient
Dosage Level(s)	
Chronic/flare-up regimen:
 
Chronic treatment 5 mg once daily (or at the dose received during participation in the parent study at the time of transition to Study CLIN-60120-452, or prior to interrupting/stopping palovarotene treatment)
 
Flare-up treatment 20 mg once daily for 4 weeks (28 days) 10 mg once daily for 8 weeks (56 days) Persistent flare-up symptoms: extension of 10 mg once daily in 4-week increments Intercurrent flare-ups (new flare-up location or marked worsening of original flare-up): 12-week flare-up treatment should be restarted
 
Chronic treatment: once daily, 5 mg or at the dose received during participation in the parent study at the time of transition to Study CLIN-60120-452 or prior to interrupting/stopping palovarotene treatment.
 
Flare-up treatment: increase in dose at the time of a flare-up (or substantial high risk traumatic event likely to lead to a flare-up) to 20 mg once daily for 4 weeks (28 days), followed by 10 mg once daily for 8 weeks (56 days) for a total of 12 weeks (84 days) (20/10 mg flare-up treatment) even if symptoms resolve earlier.
 
Flare-up treatment should begin at the onset of the first symptom indicative of a FOP flare-up or substantial high-risk traumatic event likely to lead to a flare-up. Symptoms of a FOP flare-up typically include but are not limited to localised pain, soft tissue swelling/inflammation, redness, warmth, decreased joint range of motion, and stiffness. Chronic treatment should cease at the time of initiation of flare-up treatment, re-initiation of the chronic daily treatment should occur after completion of the flare-up treatment.
 
Flare-ups can occur in the absence of any apparent causative factor, but there is a high risk that substantial traumatic events (e.g. surgery, intramuscular immunisation, mandibular blocks for dental work, muscle fatigue, blunt muscle trauma from bumps, bruises, falls or influenza-like viral illnesses), can lead to a flare-up and result in heterotopic bone formation. Flare-up treatment should be initiated at the time of such events.
 
Persistent flare-up symptoms: treatment may be extended in 4-week intervals with 10 mg palovarotene and continued until the flare-up symptoms resolve.
 
Intercurrent flare-up: if the participant experiences an intercurrent flare-up (new flare-up location or marked worsening of the original flare-up) at any time during the flare-up treatment, then the 12-week flare-up treatment should be restarted.
 
In the case of any intolerable adverse reactions, the daily dose of the chronic/flare-up regimen can be reduced (see Section 6.5).
 
Flare-up only regimen: If the participant experiences intolerable adverse reactions while taking chronic daily treatment and dose reduction does not alleviate the adverse reactions, then the participant may take palovarotene only at the time of flare-up (or substantial high-risk traumatic event).

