- A summary of the number and percentage of participants reporting a non-Serious TEAE by SOC and PT
- A summary of the number and percentage of participants reporting a non-Serious related TEAE by SOC and PT
- A summary of the number and percentage of participants reporting a TEAE leading to treatment discontinuation by SOC and PT
- A summary of the number and percentage of participants reporting a TEAE leading to dose change (increase or decrease) by SOC and PT

The below summaries will also be provided by treatment dose at time of AE onset (5mg, 10/20mg and all palovarotene):

- Overall summary of Adverse events
- A summary of the number and percentage of participants reporting a TEAE by SOC and PT

- A summary of the number and percentage of participants reporting a TEAE by maximum intensity, SOC and PT
- A summary of the number and percentage of participants reporting a TEAE by worst causality, SOC and PT
- A summary of the number and percentage of participants reporting a TEAE leading to treatment discontinuation by SOC and PT
- A summary of the number and percentage of participants reporting a TEAE leading to dose change (increase or decrease) by SOC and PT

To calculate the treatment regimen at time of AE onset, the start date of each AE will be merged with each participant dosing log. Given dosing end dates are not captured the latest dosing record prior to the AE start date will be identified. If the dosing record is either 0 mg or after treatment discontinuation the regimen will be set to “off treatment”.

AEs will be counted as follows:

- AEs summaries will be ordered in terms of decreasing frequency for SOC and PT within the overall column of each output.
- Participants with more than one AE within a particular SOC are counted only once for that SOC. Similarly, participants with more than one AE within a particular PT are counted only once for that PT.
- Participants reporting a TEAE more than once within that SOC/ PT, the TEAE with the worst-case intensity (intensity order: severe > missing > moderate > mild) will be used in the corresponding intensity summaries.
- Participants reporting a TEAE more than once within that SOC/ PT, the TEAE with the worst-case causality to study medication (order: related > missing > not related) will be used in the corresponding relationship summaries;

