### 5.8.2.2 Duration of Flare-up Treatment

For participants receiving flare-up treatment, duration of flare-up treatment (days) is defined as total flare-up cycle dosing periods (days) across all flare-up cycles. This includes any days for which the participant is receiving persistent flare-up symptom or intercurrent flare-up treatment.

For a flare-up cycle, the flare-up cycle dosing period (days) is defined as days that participants received flare-up-based treatment and is calculated as (last dose date of the flare-up cycle – first date of the flare-up cycle – days where flare-up medications were not taken/interrupted during the flare-up cycle + 1).

The mean duration of flare up treatment is defined as the total duration of flare-up treatment (across all cycles) divided by the number of flare-up treatment cycles for each individual.

The duration of persistent flare-up symptom and intercurrent flare-up treatment will be calculated in a similar manner.

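### Unless a 0 mg record is entered, the off-drug gap after a flare-up-only course counts as flare-up exposure, and adverse events in it are tabulated under 10/20 mg

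*SAP*

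**What the plan says.** SAP 5.8.2 explains that the eCRF dosing form records when each treatment period starts but not when it ends. The end is derived: "the end date will be considered as the start date of the following period", minus one day. The final record has its own rule: "For the last record, it will be the date of last dose if collected, or if not the date of last contact".

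SAP 5.8.2.2 gives the quantity wanted. The flare-up cycle dosing period is "defined as days that participants received flare-up-based treatment". It runs from the first to the last dose date of the cycle, less "days where flare-up medications were not taken/interrupted during the flare-up cycle".

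For the tables by dose at adverse event onset, SAP 5.7.2.2 says: "Given dosing end dates are not captured the latest dosing record prior to the AE start date will be identified". If that record is 0 mg, or falls after treatment discontinuation, the event is set to off treatment.

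On the chronic/flare-up regimen (Protocol 1.1 and 6.1), chronic dosing restarts once the flare-up course is complete. Protocol Table 4 also allows a flare-up-only regimen. If chronic dosing is not tolerated and dose reduction does not help, "then the participant may take palovarotene only at the time of flare-up (or substantial high-risk traumatic event"). SAP 5.1.1.2 makes flare-up treatment only one of the reported regimen groups.

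**The concern.** The end-date rule relies on another record following each course. On the chronic/flare-up regimen the chronic restart supplies it. On flare-up-only dosing, whether for the whole study or after chronic dosing has stopped, nothing in either document supplies it. The last record of a finished course, normally the 10 mg record, then stays open until the next flare-up.

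Three results could be affected:

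- **Exposure.** Total and mean duration of flare-up treatment would include months off drug. SAP 5.8.2.3 subtracts flare-up duration from chronic duration, so the error also reaches chronic exposure in participants who switch during the study.
- **Dose at onset.** Events starting off drug would be tabulated under 10/20 mg, including in the serious TEAE table by dose.
- **Compliance.** If SAP 5.6 uses the same derived dates, the expected dose is inflated and an adherent participant looks non-compliant.

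Safety is the primary objective, and treatment regimen is the only grouping kept from the protocol's list (SAP 2.6).

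**Working it through.** **Inputs from the documents.** A standard course is 20 mg for 28 days, then 10 mg for 56 days: 28 + 56 = 84 days, which matches the protocol's figure. A period ends at the next start minus 1; the last record ends at last dose, else last contact (SAP 5.8.2).

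**Assumptions.** The documents give no interval between courses. Assume two standard courses starting on Days 1 and 366, every capsule taken, and no 0 mg record. True exposure is 2 × 84 = 168 days, and the second course ends on Day 366 + 83 = 449.

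**Derived exposure**

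| Record | Start | Derived end, last dose collected | Days | Derived end, last dose missing and last contact Day 730 | Days |
|---|---|---|---|---|---|
| 20 mg | 1 | 28 | 28 | 28 | 28 |
| 10 mg | 29 | 365 | 337 | 365 | 337 |
| 20 mg | 366 | 393 | 28 | 393 | 28 |
| 10 mg | 394 | 449 | 56 | 730 | 337 |
| Total | | | 449 | | 730 |

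- Last dose collected: 449/168 = 2.7 times, an excess of 281 days. The mean per cycle is 449/2 = 224.5 days instead of 84.
- Last dose missing: 730/168 = 4.3 times, an excess of 562 days.

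**Other intervals, last dose collected.** If the courses start g days apart, derived exposure is g + 84 days.

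| g (assumed) | Derived days | Ratio to 168 |
|---|---|---|
| 120 | 204 | 1.21 |
| 182 | 266 | 1.58 |
| 365 | 449 | 2.67 |
| 547 | 631 | 3.76 |
| 730 | 814 | 4.85 |

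**Dose at onset.** In the main example the participant is off drug from Day 85 to Day 365. The latest earlier record for an event starting then is the 10 mg record of Day 29, so the event goes to 10/20 mg.

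**Compliance, if SAP 5.6 uses these dates.**

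- Dose taken: 2 × (28 × 20 + 56 × 10) = 2240 mg.
- Expected, last dose collected: 560 + 3370 + 560 + 560 = 5050 mg; 2240/5050 = 44%.
- Expected, last dose missing: 560 + 3370 + 560 + 3370 = 7860 mg; 2240/7860 = 28%.

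Both fall in the SAP's <80% category, although every capsule was taken.

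**When the error does not arise**

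- A 0 mg record at the end of each course gives 168 days at every interval above.
- A 5 mg restart on Day 85 gives 168 flare-up days, so the rule works for the chronic/flare-up regimen.
- A single course with the last-dose date collected gives 84 days. If that date is missing, a last contact on Day 365, 730 or 1095 gives 365, 730 or 1095 days.

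**The case against.** The strongest defence is that the SAP already has the tools to close a course. SAP 5.7.2.2 expects 0 mg rows on the dosing log, and such a row would also end the preceding period under SAP 5.8.2. SAP 5.8.2.2 defines the right quantity and deducts untaken days. The eCRF completion instructions, which are not among these documents, may require a 0 mg row at course end.

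This makes the error conditional but does not remove it. Neither document requires or derives a 0 mg record when a course is completed. Finishing a course is not treatment discontinuation: permanent discontinuation means withdrawal from the study (Protocol 7.1 and 7.1.3), whereas a flare-up-only participant stays in. The deduction covers days within the cycle, while the gap comes after it, and no source for untaken days is named.

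A reader might infer more than the documents support:

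- **That only a following record ends a period, or that misassignment is certain.** The last record has its own rule, and the rest depends on how sites record course end.
- **That the error is generally fourfold.** In the main example, 4.3 times needs a missing last-dose date as well as a missing 0 mg record.
- **That compliance is certainly wrong.** SAP 5.6 refers to a section 5.6.6 that does not exist, and nothing there says its cycle dates come from SAP 5.8.2.
- **That only the flare-up-only column is affected.** SAP 5.1.1.2 classifies on all dosing records, so in-study switchers would probably fall under chronic and flare-up.

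The consequences are also bounded. The TEAE tables count participants and do not use exposure-adjusted rates, and all analyses are descriptive. Flare-up-only dosing is a fallback, so few participants may be involved.

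**Conclusion.** The concern stands as a conditional flaw in a stated rule. For a completed flare-up-only course with no 0 mg record, SAP 5.8.2 counts the gap before the next course as exposure. This contradicts SAP 5.8.2.2, and SAP 5.7.2.2 places events in the gap under 10/20 mg.

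With two standard courses 120 to 730 days apart and the last dose collected, derived exposure is 1.2 to 4.9 times the truth. Those intervals are assumed. The compliance figures rest on the further assumption that SAP 5.6 uses the same dates. The number of participants affected is not given and may be small, and overall TEAE incidence does not change. The point should be settled before database lock because the dose-at-onset and exposure tables support the primary safety objective and the remedy is cheap.

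**What to change.** 1. Before database lock, query a 0 mg record or a course end date for every flare-up course not followed by a chronic dosing record. This is the preferred route because it uses observed data.
2. State in SAP 5.8.2, 5.6 and 5.7.2.2 that days after that date are excluded from flare-up exposure and expected dose, and count as off treatment for adverse event onset. Correct the reference to section 5.6.6 at the same time.
3. If the date cannot be obtained, end the period at the earliest of: next record minus 1; date of last dose; and the course end recorded as planned for that participant. Count days already taken in the parent study and any recorded extensions or restarts, and flag the date as derived. A flat 84-day cap would be wrong for participants who enter mid-course and complete a parent-study course (Protocol 1.1 and 6.1).
4. Reconcile SAP 5.8.2.1, which takes last contact as the last dose date, with SAP 5.8.2, which uses the collected last-dose date first.

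The cost is a small data query, a few sentences in the SAP and a minor programming change.

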##### 5.8.2.1 *Total Duration of Treatment*

Total duration of treatment is defined as (last dose date of IMP administration of palovarotene in Study CLIN-60120-452 - first dose date of IMP administration of palovarotene in Study CLIN-60120-452 + 1). The first dose date will be the start date of the first record in eCRF Dosing Form and the last dose date will be the date of last contact.

### 5.8.2.2 Duration of Flare-up Treatment

For participants receiving flare-up treatment, duration of flare-up treatment (days) is defined as total flare-up cycle dosing periods (days) across all flare-up cycles. This includes any days for which the participant is receiving persistent flare-up symptom or intercurrent flare-up treatment.

For a flare-up cycle, the flare-up cycle dosing period (days) is defined as days that participants received flare-up-based treatment and is calculated as (last dose date of the flare-up cycle – first date of the flare-up cycle – days where flare-up medications were not taken/interrupted during the flare-up cycle + 1).

The mean duration of flare up treatment is defined as the total duration of flare-up treatment (across all cycles) divided by the number of flare-up treatment cycles for each individual.

The duration of persistent flare-up symptom and intercurrent flare-up treatment will be calculated in a similar manner.

### 5.8.2.3 Duration of Chronic Treatment

Based on the study design, participants are assumed to be on non-flare-up-based treatment from the date they received the first non-flare-up treatment unless they receive flare-up-based treatment. Thus, duration of non-flare-up treatment (days) will be calculated as (last non-flare-up treatment date - first non-flare-up treatment date – duration of flare-up treatment (days) - days where non-flare-up medications were not taken/interrupted + 1).

### 5.8.3 Laboratory Data

Amylase, lipase, AST, ALT and fasting triglyceride levels from the EOS of parent studies and centrally measured (or locally measured of the inclusion visit is >1 month than the end of the parent study visit) will be used at the Inclusion Visit for screening purposes only. [Note: Amylase, lipase, AST, ALT and fasting triglyceride levels at the EOS of parent studies will be transferred from the parent study database.]

All laboratory data will be presented in the units of International System of Units (SI), summarised descriptively for the inclusion visit and listed.

### 5.8.4 C-SSRS

A summary of the number and percentage of participants with any type of suicidal ideation or behaviour (yes/no) will be presented at each visit. The number of questionnaires completed and the CSSRS suicidal ideation score will be also presented at each visit. Suicidal ideation includes the categories:

- Wish to be dead
- Non-specific active suicidal thoughts
- Active suicidal ideation with any methods (not plan) without intent to act
- Active suicidal ideation with some intent to act, without specific plan
- Active suicidal ideation with specific plan and intent

Whereas suicidal behaviour includes:

- Preparatory acts or behaviour
- Aborted attempt
- Interrupted attempt
- Non-fatal suicide attempt
- Completed suicide

In addition, a shift table from the inclusion visit to each post-inclusion visit of no suicidal ideation or behaviour, any suicidal ideation and any suicidal behaviour will be presented. Participants with both suicidal ideation and suicidal behaviour are included in the suicidal behaviour category.

Similarly, a shift table of maximum suicidal ideation assessments from the inclusion visit to each post-inclusion visit will be presented. Maximum refers to the maximum C-SSRS suicidal ideation score during treatment (0 = least severe, 5 = most severe) where 0=No Suicidal Ideation, 1=Wish to be Dead, 2=Non-specific Active Suicidal Thoughts, 3=Active Suicidal Ideation with Any Methods (Not Plan) without Intent to Act, 4=Active Suicidal Ideation with Some Intent to Act, without Specific Plan, and 5=Active Suicidal Ideation with Specific Plan and Intent.

All participants who report any type of suicidal ideations in the C-SSRS or any suicidal behaviour during the study will be presented in listings.

### **5.8.5 *Linear Height and Body Weight***

Actual values and mean changes from baseline in height/linear height (cm) and body weight (kg) will be presented descriptively at each visit for the FAS/SAS. For participants under the age of 18 years, the mean of triplicate height measurements will be used.

In addition, for participants aged <18 years at study inclusion, height velocity [cm/year] and linear height z-score actual values and changes from inclusion visit will be summarised descriptively at each visit for the FAS/SAS.

The calculation of height velocity will be performed as follows: ((Current Height – Previous Height)/(duration (days)=(current date – previous date))) \* 365.25 = Annualized height velocity (cm/year). In addition to providing the calculated height velocities per time period for each participant at each visit, the data will also be categorized according to the following three categories: <4 cm/year; 4 to 5 cm/year; and >5 cm/year.

The linear height z-scores will be calculated using the reference population from the Centers for Disease Control and Prevention (CDC). See Appendix 7.2 for further details.

A listing of all linear height and body weight parameters will be presented.

### **5.8.6 *Vital Signs***

Vital signs include systolic blood pressure [mmHg], diastolic blood pressure [mmHg], heart rate [beats/min] and respiratory rate [breathes/min].

A summary of all vital sign variables (vital sign raw values and changes from inclusion visit) will be calculated for each visit for the FAS/SAS with descriptive statistics.

Potentially clinically significant (PCS) values are predefined criteria/thresholds presented in Appendix A2.

New-onset PCS values are defined as values that were not PCS at baseline and were PCS post-baseline. New-onset PCS values post-baseline will be summarised with counts and percentages. In addition a shift table from inclusion visit to each post-inclusion visit will be presented by abnormality (low, normal, high) as defined by the below criteria:

In addition a shift table from inclusion visit to each post-inclusion visit will be presented by abnormality (low, normal, high) as defined by the below criteria:

	Low	Normal	High
Systolic blood pressure	<86 mmHg	86 – 180 mmHg	>180 mmHg

	Low	Normal	High
Diastolic blood pressure	<48 mmHg	48 – 110 mmHg	>110 mmHg
Heart rate	<45 bpm	45 – 125 bpm	>125 bpm
mmHg = millimeters of mercury, bpm = beats per minute.			

A listing of all vital sign data and PCS values will be presented.

### **5.8.7 Physical Examination**

A summary of physical examination results (Normal, Abnormal non-clinically significant and abnormal clinically significant) will be provided by body system at the inclusion visit for the FAS/SAS with descriptive statistics.

A listing of physical examination data will be provided.

### **5.8.8 Spinal Health Assessment**

A listing of Spinal health assessment data will be provided using the FAS/Safety Set.

